#### 7.2.6.3.2 Exogenous Insulin Independence

For subjects in Cohort 2, exogenous insulin independence will be defined in two ways.

First, achieving exogenous insulin independence will be defined as having an exogenous insulin dose of 0 for a minimum of any 14 consecutive days during the study, based on the data from exogenous daily insulin dose logs. Days that are missing or blank on the insulin log are not considered to be 0 values.

The second definition of exogenous insulin independence includes having an exogenous insulin dose of 0 for a minimum of any 14 consecutive days (the first definition of insulin independence) in addition to having HbA1c  $\leq$  7.0%, and (2-hour or 4-hour) MMTT fasting (at the start of the MMTT) glucose  $\leq$  125 mg/dL and 120-minute glucose  $\leq$  180 mg/dL. The HbA1c value and the MMTT glucose values will be those values obtained at a clinic visit that is closest temporally to the 14 consecutive days of 0 exogenous insulin dose. Depending on when the 0 doses of insulin begin, it is possible that the closest value temporally for HbA1c may be from a different clinic visit than the closest value temporally for glucose from the MMTT.

## 7.2.6.4 Percent of Time Spent with Blood Glucose Values at Various Cut Points

Cohort 2 subjects will be provided with a CGM system by the Sponsor and are required to use the Sponsor-provided CGM during study participation. The blood glucose value cut points of <54 mg/dL,  $\geq$ 54 to <70 mg/dL,  $\geq$ 70 mg/dL to  $\leq$ 180 mg/dL,  $\geq$ 180 mg/dL and >250 mg/dL will be assessed.

The assessment of blood glucose cut points will be performed three ways: over the entire 24-hour time period, over the nocturnal (CGM value below/above the cut point occurs between 12 a.m. - 6 a.m.) time period, and over the daytime (CGM value below/above the cut point occurs between 6 a.m. - 12 a.m.) time period.

Baseline CGM data will be utilized to calculate percentages of time spent with blood glucose values at the various cut points for up to 28 days, starting at Day -1 (i.e., the day prior to implant) and working backwards for up to 28 days (through Day -28). For instances in which the available pre-implant data provides less than 28 days of data, post-implant data will be used, from Day 4 forward until 28 days of data are available. In addition, the CGM data from the 14 days prior to each scheduled clinic visit will be used to calculate percentages spent with blood glucose values at the various cut points for these visits. For all timepoints (baseline and on-study), data should not be used if an SOGCT (baseline only) or MMTT was performed on that day.

## 7.2.6.5 Frequency of HEs using Subject-Reported Diary Data

HE data collected from the subject-completed diaries will be used for assessment of efficacy. Investigators will review the HE logs in the diary at each study visit. Blank values in the HE log are considered to be 0 values.

HEs will be classified in six ways: total HEs, severe HEs (SHEs), nocturnal HEs, severe nocturnal HEs, daytime HEs, and severe daytime HEs. Total HEs are HEs that occur at any time during the 24-hour period; SHEs are HEs requiring the aid of another person to administer carbohydrates, glucagon, or other resuscitative assistance any time during the 24-hour period. Nocturnal HEs are HEs that start during the 12 a.m. -6 a.m. period; severe nocturnal HEs are SHEs that start during the 12 a.m. -6 a.m. period. Daytime HEs are HEs that start during the 6 a.m. -12 a.m. period; severe daytime HEs are SHEs that start during the 6 a.m. -12 a.m. period.

The baseline average weekly frequency of subject-reported HEs, SHEs, nocturnal HEs, severe nocturnal HEs, daytime HEs and severe daytime HEs will be calculated using up to 28 days of data. The baseline average weekly frequency will be calculated using data starting at Day -1 (i.e., the day prior to implantation) and working backwards for up to 28 days (through Day -28). For instances in which the available pre-implant data provides less than 28 days of data, post-implant data will be used from Day 4 forward until 28 days of data are available. Data from days on which the Screening SOGCT or the MMTT was performed will not be used in the calculation.

The total number of HEs, SHEs, nocturnal HEs, severe nocturnal HEs, daytime HEs, and severe daytime HEs occurring in the 14 days prior to each specified time point (Weeks 16, 20, 26, 39, and 52) will be used to calculate the weekly frequency of total HEs, SHEs, nocturnal HEs, severe nocturnal HEs, daytime HEs, and severe daytime HEs, respectively, at the specified time point. Data for HEs/SHEs should not be used if an MMTT was performed on that day.

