7.16. Definition, Classification, and Management of Hypoglycemic Events (HEs) – Cohort 2 Only

All SMBG or CGM values of <54 mg/dL (<3.0 mmol/L) must be captured by the subject in the diary as an HE. Additionally, if a subject does not have a blood glucose value available, but has symptoms of an HE, the HE must still be captured in the diary as an HE. For any SHE experienced between scheduled clinic visits, the subject must enter the data on the diary and also contact the study site to provide details of the event.

At Visit 3 (Day 1) and each clinic visit thereafter, the Investigator will review the subject's HE entries on the study diary, CGM and SMBG values, and any other supportive information. Each HE occurring beyond Visit 2 (Week -4) must be captured on a CRF and will be classified based on the definitions below. Per standards of care, the Investigator should also evaluate any HEs

occurring between Visit 1 and Visit 2 reported by the subject, but they are not captured on the CRF.

- Severe hypoglycemic event (SHE): an event requiring assistance of another person to actively administer carbohydrate, glucagon, or other resuscitative actions.
- Documented symptomatic hypoglycemia: an event accompanied by typical symptoms of hypoglycemia with documented plasma glucose measured at <70 mg/dL (3.9 mmol/L).
- Asymptomatic hypoglycemia: an event with measured plasma glucose of <54 mg/dL (3.0 mmol/L) in the absence of symptoms.
- Probable symptomatic hypoglycemia: subject reports typical hypoglycemia symptoms but does not provide a temporally-associated SMBG or CGM value.
- Pseudo-hypoglycemia or relative hypoglycemia: an event is reported by subject, but the associated SMBG or CGM value is ≥70 mg/dL (3.9 mmol/L).

The frequency of HEs will be captured and counted over the course of Cohort 2. In addition, the Sponsor will consider defining additional HEs using the CGM data on an exploratory basis. The Investigator may request an Unplanned Visit to review study diary entries and determine if modifications in insulin dosing are necessary to reduce the occurrence of HEs. Based on available information, the Investigator should make appropriate decisions regarding the insulin therapy to mitigate HE occurrences.

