8.2. Serious Adverse Events (SAE)

An SAE is any untoward medical occurrence meeting at least one of the following criteria:

- Results in death:
- Is life-threatening (immediate risk of death);
- Requires in-patient hospitalization or prolongation of existing hospitalization;
- Results in persistent or significant disability/incapacity (substantial disruption of the ability to conduct normal life functions);
- Results in congenital anomaly/birth defect;
- Constitutes an Important Medical Event in the opinion of the Investigator and/or Sponsor.

Medical and scientific judgment is exercised in determining whether an event is an important medical event. An important medical event may not be immediately life threatening and/or result in death or hospitalization. However, if it is determined the event may jeopardize the subject or may require intervention to prevent one of the other SAE criteria, the important medical event should be reported as serious.

Based on the definition above, severe hypoglycemic events (SHE) may or may not be reported as SAEs and will be classified at the Investigator's discretion. In all instances, SHEs are to be recorded on the hypoglycemic event (HE) CRF.

AEs resulting in hospitalization or prolongation of a hospitalization are considered serious. Any formal admission (even if less than 24 hours) to a healthcare facility meets these criteria. Admission also includes transfer within the hospital to an acute or intensive care unit (e.g., from the psychiatric wing to a medical floor, medical floor to a coronary care unit, neurological floor to a tuberculosis unit).

Hospitalization does not include the following:

• Rehabilitation facilities;

- Hospice facilities;
- Respite care (e.g., caregiver relief);
- Skilled nursing facilities;
- Nursing homes;
- Emergency room visits;
- Outpatient surgical procedures.

Hospitalization or prolongation of hospitalization in the absence of a precipitating, clinical AE is not in itself an SAE. Examples include:

- Admission for treatment of a pre-existing condition not associated with the development of a new AE or with a worsening of the preexisting condition (e.g., for work-up of persistent pre-treatment lab abnormality);
- Social admission (e.g., subject has no place to sleep);
- Administrative admission (e.g., for yearly physical exam);
- Protocol-specified admission during a study (e.g., for a procedure required by the study protocol);

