Change from baseline in frequency of hypoglycemic events (24-hour; daytime [start between 6 a.m. – 12 a.m.]; nocturnal [start between 12 a.m. – 6 a.m.]) at Weeks 16, 20, 26, 39, and 52 will each be analyzed using ANCOVA, with treatment group as a factor and the relevant baseline as a covariate. This analysis will be performed separately using HEs from the patient-reported diary and from CGM.

The number and percent of subjects free of severe hypoglycemic events between study visits (Weeks 16-20, Weeks 20-26, Weeks 26-39, Weeks 39-52, and Weeks 16-52) will each be analyzed using Fisher's exact test. The number and percent of subjects in each treatment group and the p-value from the Fisher's test will be provided (at each time point, where appropriate). These analyses will be performed separately using HEs from patient-reported diary and HEs from CGM.

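### The SAP's only assistance-based analysis of severe hypoglycaemia for efficacy rests on the subject diary, with blanks scored as zero, and does not use the hypoglycaemic-event CRF on which the protocol requires every severe event

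*SAP*

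**What the plan says.** **Protocol.** Section 7.16 (Cohort 2) has the investigator review diary entries, CGM and SMBG values and other supporting information from Visit 3 onward. It then requires: "Each HE occurring beyond Visit 2 (Week -4) must be captured on a CRF and will be classified based on the definitions below". Section 8.2 adds: "In all instances, SHEs are to be recorded on the hypoglycemic event (HE) CRF". For a severe event between visits, section 7.16 asks the subject both to log it and to contact the site. One of the five classes in section 7.16 is pseudo-hypoglycaemia, where "an event is reported by subject, but the associated SMBG or CGM value is ≥70 mg/dL".

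**SAP.** Section 7.2.6.5 names the diary as the efficacy source: "HE data collected from the subject-completed diaries will be used for assessment of efficacy". It adds "Investigators will review the HE logs in the diary at each study visit" and "Blank values in the HE log are considered to be 0 values". Its SHE definition, help from another person, agrees with the protocol. Total events are defined by time of day only: "Total HEs are HEs that occur at any time during the 24-hour period". Section 7.2.6.6 defines a CGM severe event as glucose below 54 mg/dL, with a 15-minute minimum duration. On the SHE-free proportions, section 7.3.7.3 says: "These analyses will be performed separately using HEs from patient-reported diary and HEs from CGM". The HE-frequency ANCOVA uses the same two sources. The SAP text does not mention the HE CRF or the investigator's classification.

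**The concern.** The protocol creates a reviewed and classified record of severe events, fed by more than one route. The efficacy analysis uses the subject's own log instead and treats a gap in that log as evidence of no event. SAP 7.2.6.3 takes the opposite line for insulin, where a blank is not zero.

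A severe event is one in which the subject needed another person's help, so it may be reported by telephone or at a visit without being logged. Protocol 7.13 itself provides for repeated failure to complete the diary. At stake are the SHE-free percentages from Week 16 onward and the weekly SHE frequencies. An omitted event can only raise the SHE-free percentage, so errors of this kind do not average out.

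**Working it through.** The plan gives no figure on this point to reproduce. The check compares the texts and then sizes the effect.

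**1. Trace one event.** Suppose a subject needs assistance, telephones the site and does not log the event.

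- HE CRF (Protocol 7.16 and 8.2): recorded as an SHE.
- Diary (SAP 7.2.6.5): blank, so 0 events.
- Diary SHE-free analysis (SAP 7.3.7.3): the subject counts as SHE-free, if no other SHE is logged in that interval.
- CGM SHE-free analysis (SAP 7.2.6.6 and 7.3.7.3): an event only if the readings meet the below-54 mg/dL and 15-minute rule. An assisted event at 54 mg/dL or above, or with no sensor data, is missed. An unassisted low below 54 mg/dL does count. CGM therefore measures something else and cannot stand in for the CRF.

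The SAP has no rule for reconciling diary and CRF.

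**2. Size of one omission.** Shift in SHE-free percentage = 100/n. Cohort 2 has up to 40 subjects (SAP 7.1). Treatment group is the number of VC-01-DF units initially implanted (SAP 5). Group sizes are not given, so those below 40 are assumptions.

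- n = 40: 100/40 = 2.5 points
- n = 20: 100/20 = 5 points
- n = 10: 100/10 = 10 points
- n = 5: 100/5 = 20 points

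**3. Several events.** Let k of 40 subjects have an SHE on the CRF, and let m be the chance that the diary lacks it (both assumed). Expected diary SHE-free = 100 × (40 − k(1 − m))/40.

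| k | CRF SHE-free | m = 10% | m = 25% | m = 50% |
|---|---|---|---|---|
| 2 | 95% | 95.5% | 96.25% | 97.5% |
| 4 | 90% | 91% | 92.5% | 95% |
| 8 | 80% | 82% | 85% | 90% |

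For k = 4 and m = 25%: 100 × (40 − 3)/40 = 92.5%.

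**4. Fisher's test.** In an assumed 20 versus 20 comparison, 5 versus 0 subjects with an SHE gives p = 0.047. With one omitted, 4 versus 0 gives p = 0.106. Such p-values are descriptive under SAP 7.3.7.3.

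**5. Total events.** SAP 7.2.6.5 sets no glucose criterion for diary events and does not say whether pseudo-hypoglycaemia entries count. If one did, it would add 7/14 = 0.50 events per week to a 14-day visit window and 7/28 = 0.25 per week to a full 28-day baseline.

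**The case against.** **Does the diary already mean reviewed data?** Protocol 7.16 makes diary entries an input to the CRF, and SAP 7.2.6.5 mentions investigator review, so the SAP could mean diary events after site review. SAP 7.2.2 also says data are summarized by the eCRF in which they were collected. The first point is a fair reading of intent, but no rule lets the review add or reclassify an event. The eCRF sentence concerns assignment to visits and does not bring the HE CRF into these analyses.

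**Is a lost event likely?** There are safeguards: daily entry, dual reporting of SHEs, review at each visit and possible automated alerts (Protocol 7.13 and 7.16). The documents give no reason to expect frequent divergence. That stands, and the omission rates above are assumptions.

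**Stronger readings a reader might infer.**

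- *That the SAP counts pseudo-hypoglycaemia as events.* It is silent. Protocol 7.16 lists that class among its HE classes and does not require diary entries at 70 mg/dL or above. Such entries cannot enter the CGM count, and a constant rate of them would largely cancel in change from baseline.
- *That real severe events disappear and the product looks safer.* SAP 7.3.7.2 plans a safety summary of hypoglycaemic events, without naming its source. SAP 5 lists all collected data, and Protocol 8.6 and 13.6 have SHE-based criteria of their own. An SHE on the CRF would still be listed.
- *That repeated diary entries for one low must be merged by the SAP's 60-minute CGM rule.* That is a preference. Moving to the CRF does not settle it, because the protocol's below-54 mg/dL capture rule feeds the CRF as well.

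**Conclusion.** The point holds for severe events. As written, the only efficacy analysis that uses the assistance definition depends on the diary, and an SHE on the CRF but missing from the diary counts as no event. The size is 2.5 points per omitted subject if n = 40, and more in smaller groups (10 points if n = 10, an assumed size). This assumes that the subject has no other logged SHE in the interval. How often omission would occur cannot be judged from the documents.

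For total events the point is limited to specification: the source and the classes that count should be stated.

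This is a worthwhile improvement, not a must-fix. The HE-frequency and SHE-free endpoints are secondary, appear in SAP 4.2 but not among the efficacy endpoints in Protocol 2.2.2, and carry descriptive p-values in an open-label trial that tests no hypotheses. The primary C-peptide analysis is unaffected. If the safety summary does draw on the CRF, safety and efficacy SHE counts could also differ without explanation, which is a further reason to name the source.

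**What to change.** In SAP 7.2.6.5 and 7.3.7.3:

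1. Count as an SHE any event recorded as severe on the HE CRF, reconciled with diary and SAE records. Use this for the SHE-free proportions and SHE frequencies.
2. Keep the diary-only result as a sensitivity analysis.
3. Take total HEs from the investigator-classified CRF events, and report counts with and without the pseudo-hypoglycaemia class (70 mg/dL or above).
4. Keep the CGM analysis separate, as planned.
5. Optionally, state whether diary entries that start within 60 minutes of each other are merged.

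The cost is SAP wording, programming and a reconciliation step before database lock. The protocol already requires the CRF, so no new data and no change to clinical management are needed.

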## 7.2.6.6 Frequency of HEs using CGM Data

CGM will be utilized, based on the below specified rules, to evaluate the number of hypoglycemic episodes (number of times blood glucose falls below 70 mg/dL) and the number of severe hypoglycemic events (number of times blood glucose falls below 54 mg/dL) for each subject:

- A set of CGM readings < 70 mg/dL or <54 mg/dL, with a minimum overall duration of 15 minutes
- Up to two consecutive readings >= 70 mg/dL (or >= 54 mg/dL for separate summary) are allowed within the same episode
- If a subsequent episode starts within 60 minutes of the start of the previous episode, then they are combined and counted only as one episode

The total number (over the entire 24-hour time period) of episodes will be calculated as well as the number of nocturnal (starts during the 12 a.m. - 6 a.m. period) episodes and the number of daytime (starts during the 6 a.m. to 12 a.m.) episodes.

Baseline CGM-reported HE data will be calculated using up to 28 days of data. Baseline CGM-reported HEs will be recorded starting at Day -1 (i.e., the day prior to implant) and working backwards for up to 28 days (through Day -28). For instances in which the available pre-implant data provides less than 28 days of data, post-implant data will be used from Day 4 forward until 28 days of data are available. These data will be used to calculate the baseline number of weekly total episodes, weekly nocturnal episodes, and weekly daytime episodes. In addition, the CGM data from the 14 days prior to each scheduled clinic visit will be used to calculate the number of weekly total episodes, the number of weekly nocturnal episodes, and the number of weekly daytime episodes for each of these visits. For baseline and on-study time points, data from days on which an SOGCT (baseline only) or MMTT was performed should not be used.

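### The SAP calls CGM episodes below 54 mg/dL severe, so the CGM version of the SHE-free percentage does not measure the endpoint it is named for

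*SAP*

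**What the plan says.** SAP 7.2.6.6 derives two counts from CGM. Readings below 70 mg/dL give hypoglycemic episodes. The lower threshold gives "the number of severe hypoglycemic events (number of times blood glucose falls below 54 mg/dL". An episode must last at least 15 minutes, may contain up to two consecutive readings back at or above the threshold, and is merged with the previous one if it starts within 60 minutes of that one's start. Nothing in the rule refers to symptoms or to help received.

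One section earlier, SAP 7.2.6.5 says "SHEs are HEs requiring the aid of another person to administer carbohydrates, glucagon, or other resuscitative assistance". Protocol 7.16 defines an SHE as "an event requiring assistance of another person to actively administer carbohydrate, glucagon, or other resuscitative actions", with no glucose threshold. The same protocol section says "All SMBG or CGM values of <54 mg/dL (<3.0 mmol/L) must be captured by the subject in the diary as an HE", and its asymptomatic class is "an event with measured plasma glucose of <54 mg/dL (3.0 mmol/L) in the absence of symptoms".

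SAP 4.2 lists the percentage of subjects free of severe events between visits, from Week 16, as a secondary efficacy endpoint. SAP 7.3.7.3 tests it with Fisher's exact test and adds: "These analyses will be performed separately using HEs from patient-reported diary and HEs from CGM".

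For the diary count, SAP 7.2.6.5 says "Blank values in the HE log are considered to be 0 values". It uses up to 28 days at baseline and the 14 days before Weeks 16, 20, 26, 39 and 52, and leaves out days with an MMTT (and, at baseline, the SOGCT). It gives no minimum number of days and no divisor. The insulin rules in SAP 7.2.6.3 and 7.2.6.3.1 differ: a blank is not zero, at least 4 days are needed, and the sum is divided by the number of days with doses.

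**The concern.** The word severe has two meanings in adjacent SAP sections. A symptom-free reading of 50 mg/dL lasting 20 minutes is, under the protocol, an ordinary diary event classed as asymptomatic. Under SAP 7.2.6.6 it is a severe event. Two results with the same endpoint name would then answer different questions. The CGM figure could not confirm or contradict the diary figure, and a reader of the report could take it for SHEs in the protocol's sense.

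The diary count raises a lesser question. An empty HE log can mean that nothing happened or that the diary was not used. Read literally, the rule makes both event-free, and without a stated divisor two programmers could produce different weekly rates from the same data.

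**Working it through.** The plan states no figure for either point, so there is nothing to reproduce. The first step is to compare the definitions; the numbers after that use assumed rates and show only how the rules behave.

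**Definitions.** In Protocol 7.16 and SAP 7.2.6.5 the criterion is assistance. In SAP 7.2.6.6 it is glucose below 54 mg/dL for 15 minutes. Neither implies the other: most low readings may need no help, and the assistance definition does not require a measured glucose value. The two cannot be the same endpoint.

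**Size of the gap.** Let r be CGM episodes below 54 mg/dL per week, p the share needing help, and w the weeks in the interval (4 for Weeks 16-20, 36 for Weeks 16-52). Assume Poisson events and that every assisted event is one of the CGM episodes. Then free by CGM = exp(-r x w), and free of assisted events = exp(-r x p x w).

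| r | w | Free by CGM | Free of assisted events, p = 1 / 5 / 10% |
|---|---|---|---|
| 0.02 | 36 | 48.7% | 99.3 / 96.5 / 93.1% |
| 0.05 | 36 | 16.5% | 98.2 / 91.4 / 83.5% |
| 0.1 | 36 | 2.7% | 96.5 / 83.5 / 69.8% |
| 0.1 | 4 | 67.0% | 99.6 / 98.0 / 96.1% |

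For example, exp(-0.1 x 36) = exp(-3.6) = 0.027 and exp(-0.1 x 0.05 x 36) = exp(-0.18) = 0.835. In 40 subjects that is about 1 against 33. If rates vary widely between subjects (gamma, shape 1), the pair becomes 1/(1 + 3.6) = 22% and 1/(1 + 0.18) = 85%. The gap narrows but remains.

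**Diary count.** Assume a true 2 HEs per week, with events on unused days never logged. With n used days out of 14 and a divisor of 14, the rate is 7 x (2/7 x n)/14: 2.00 for n = 14, 1.43 for n = 10, 1.00 for n = 7. If every event is logged whatever the other diary use, the rate is 2.00 throughout.

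For change from baseline, only the ratio of completeness matters. With a constant true rate, apparent change = cF/cB - 1, where cB and cF are the fractions of days used at baseline and follow-up:
- 100% then 80%: -20%
- 90% then 90%: 0
- 90% then 100%: +11%
- 90% then 70%: -22%

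**Divisor.** If one MMTT day is excluded from the events but left in the divisor, the on-study rate is 13/14 - 1 = 7.1% low. At baseline it is 27/28 - 1 = 3.6% low if the excluded day is not replaced. On study this needs an MMTT inside the 14 days before the visit, such as one done up to 5 days before an explant (Protocol 7.2). At baseline it is more usual, because the Visit 2 MMTT has a target of Day -28, the first day of the window.

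**The case against.** The strongest reply on the first point is that SAP 7.2.6.6 prints its threshold and episode rules and SAP 7.3.7.3 keeps the two sources apart, so a careful reader would not be misled. The calculation is indeed fully specified. But separate runs do not give an outcome the right name: both outputs would report the SAP 4.2 endpoint, and only one measures it.

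A reader might infer that the protocol confines CGM-defined events to exploratory use, since Protocol 7.16 says "the Sponsor will consider defining additional HEs using the CGM data on an exploratory basis". The documents do not support that. Protocol 7.14 assigns CGM data to secondary as well as exploratory endpoints and leaves further CGM endpoints to the SAP. A secondary CGM analysis is legitimate; only its label is wrong.

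A reader might also infer that the stopping and withdrawal criteria are affected because they use the term SHE. Protocol 7.16 defines that term by assistance, and no text feeds the SAP's CGM counts into those criteria.

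On the diary, a reader might infer that the SAP has no rule for which days count. It has one: blank is zero, test days are excluded and the windows are fixed. Blank as no event is a natural reading of an event log. Protocol 7.13 requires daily entry and review at each visit, Protocol 7.16 has the Investigator check diary events against CGM and SMBG values, and the HE-frequency analysis is repeated on CGM. These safeguards reduce the risk of lost events. They supply neither a divisor nor a minimum.

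Making days with an insulin entry the main basis would go too far. It discards logged events and could lose subjects who come off insulin and stop entering zeros. It also costs precision: at 2 HEs per week the SD of one visit's rate is the square root of 14/n, which is 1.00 for 14 days and 1.18 for 10.

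**Conclusion.** The mislabelling is an error in the text as written and needs no assumption to establish. The CGM analysis in SAP 7.3.7.3 does not measure freedom from SHEs as SAP 7.2.6.5 and Protocol 7.16 define them. How far the two results would differ depends on rates that the documents do not give. Over Weeks 16-52 the illustrations run from 48.7% against 96.5% (r = 0.02, p = 5%) to 2.7% against 83.5% (r = 0.1, p = 5%).

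The diary point is a gap in specification. It biases change from baseline only if completeness differs between baseline and follow-up, and treatment-group comparisons only if it differs by group. The documents show neither, so a reader should not infer that the diary rates will be biased. Nor does this point require replacing the planned percentages with a time-to-event method.

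All of these are secondary endpoints with descriptive p-values. The primary C-peptide endpoint is untouched.

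**What to change.** In SAP 7.2.6.6 and 7.3.7.3, rename the CGM outcome as CGM episodes <54 mg/dL and keep its analysis under that name. Report the SHE-free percentage only on the assistance definition, using the diary and the HE CRF, on which Protocol 8.2 already requires every SHE to be recorded.

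In SAP 7.2.6.5:
- Keep the present count as the main analysis, and state the rate as 7 x HEs / days included after MMTT and SOGCT days are removed, at baseline and on study.
- Report diary completeness by visit and treatment group.
- Add a sensitivity analysis restricted to days with evidence of diary use from any entry type, not insulin alone, with a minimum number of days. The 4 days already used for insulin is a ready model. Say how downloaded entries count as evidence, and list days that qualify only through an HE entry, because such days push the rate up.

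The cost is SAP wording and programming, with no new data. Some visits will drop out of the sensitivity analysis. With a 4-day minimum and each of 14 days used independently with probability 50%, (1 + 14 + 91 + 364)/16,384 = 2.9% would fall short. The main analysis loses none.
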